## 8.4 Recording Adverse Events

**If no SAE** is associated with the special situation, the special situation should be recorded in the CRF and sent annually to the Company.

---

These safety events may not meet the definition of an adverse event; however, the Parties agree that for reporting purposes, they are deemed to be adverse events.

### **“Safety Assessment and Follow-Up**

#### **8.4.1 Relationship to Study Intervention**

The relationship to study intervention or study participation must be assessed and documented for all adverse events. Evaluation of relatedness must consider etiologies such as natural history of the underlying disease, concurrent illness, concomitant therapy, study-related procedures, accidents, and other external factors.

The following guidelines are used to assess relationship of an event to study intervention:

1. Related (Possible, Probable, Definite)
  - a. The event is known to occur with the study intervention.
  - b. There is a temporal relationship between the intervention and event onset.
  - c. The event abates when the intervention is discontinued.
  - d. The event reappears upon a re-challenge with the intervention.
2. Not Related (Unlikely, Not Related)
  - a. There is no temporal relationship between the intervention and event onset.
  - b. An alternate etiology has been established.

#### **8.4.2 Expectedness**

The PI is responsible for determining whether an AE is expected or unexpected. An AE will be considered unexpected if the nature, severity, or frequency of the event is not consistent with the risk information previously described for the intervention. Risk information to assess expectedness can be obtained from preclinical studies, the investigator's brochure, published medical literature, the protocol, or the informed consent document.

#### **8.4.3 Severity of Event**

Adverse events will be graded for severity according to the Common Terminology Criteria for Adverse Events (CTCAE) version 5.0

#### **8.4.4 Intervention**

Any intervention implemented to treat the adverse event must be documented for all adverse events.

## 8.5 Safety Reporting

### 8.5.1 Reporting to IRB

#### 8.5.2 Unanticipated Problems

All incidents or events that meet criteria for unanticipated problems (UAPs) as defined in Section 8.1.2 require the creation and completion of an unanticipated problem report form (OHR-20).

UAPs that pose risk to participants or others, and that are not AEs, will be submitted to the IRB on an OHR-20 form via the eazUP system within 10 working days of the investigator becoming aware of the event.

UAPs that do not pose risk to participants or others will be submitted to the IRB at the next continuing review.

##### 8.5.2.1 Adverse Events

Grade 1 AEs will be reported to the IRB at continuing review.

Grade 2 AEs will be reported to the IRB at the time of continuing review.

##### 8.5.2.2 Serious Adverse Events

SAEs will be reported to the IRB on OHR-10 forms via the electronic reporting system (eSAEY) according to the required time frames described below.

Grade 3-4 AEs that are unexpected and deemed to be at least possibly related to the study will be reported to the IRB within 2 working days of knowledge of the event.

Grade 3-4 AEs that are deemed unrelated to the study will be reported to the IRB within 5 working days.

Grade 5 AEs will be reported to the IRB within one working day of knowledge of the event.

All SAEs will be submitted to the IRB at continuing review, including those that were reported previously.

### 8.5.3 Reporting to SKCC DSMC

All AEs and SAEs, safety and toxicity data, and any corrective actions will be submitted to the DSMC per the frequency described in the SKCC DSMP. The report to the SKCC DSMC will also include any unanticipated problems that in the opinion of the PI should be reported to the DSMC.

For expedited reporting requirements, see table below:  
DSMC AE/SAE Reporting Requirements

	Grade 1	Grade 2		Grade 3				Grades 4 and 5
	Unexpected and Expected	Unexpected	Expected	Unexpected		Expected		Unexpected and Expected
				With Hospitalization	Without Hospitalization	With Hospitalization	Without Hospitalization	
Unrelated Unlikely	Reviewed at Quarterly DSMC Meeting and IRB Annual Review	Reviewed at Quarterly DSMC Meeting and IRB Annual Review	Reviewed at Quarterly DSMC Meeting and IRB Annual Review	5 Working Days	Reviewed at Quarterly DSMC Meeting and IRB Annual Review	5 Working Days	Reviewed at Quarterly DSMC Meeting and IRB Annual Review	Phase I - 48 Hours (Death: 24 Hours)
Possible Probably Definite	Reviewed at Quarterly DSMC Meeting and IRB Annual Review	Reviewed at Quarterly DSMC Meeting and IRB Annual Review	Reviewed at Quarterly DSMC Meeting and IRB Annual Review	48 Hours (Death: 24 Hours)	Phase I - 48 Hours	48 Hours (Death: 24 Hours)	Reviewed at Quarterly DSMC Meeting and IRB Annual Review	Phase I and Phase II - 48 Hours (Death: 24 Hours)

## 8.5.4 Reporting to Funding Company

### 8.5.4.1 **Sponsor Responsibilities**

#### 8.5.4.1.1 **Health Authority**

The Institution/Investigator shall be solely responsible for complying, within the required timelines, with any safety reporting obligation towards the competent health authorities, the Ethics Committees (EC) or Independent Review Board (IRB) and the participating (co- or sub-) investigators.

#### 8.5.4.1.2 **General**

The Institution / Investigator shall notify Janssen immediately in case of a suspension of recruitment or premature stop of the concerned clinical study because of a safety concern; preferably by means of a telephone contact with the Company Representative, alternatively by email within twenty-four (24) hours of the decision.

Institution / Investigator shall provide to the Janssen copies of any and all relevant extraordinary (not including routine initial or follow-up ICSR submission) correspondences with health authorities and ethics committees regarding any and all serious adverse events (irrespective of the association with the Janssen Product(s) Under Study). Copies of such correspondence shall be provided within 24 hours of such report or correspondence being sent to applicable health authority.

Training: Institution of the Study shall be responsible for training the Study personnel (including the Investigator) on managing safety information arising from the Study according to agreed procedures and the requirements of this Agreement.

Management of Safety Data: The Institution and Investigator will provide safety information arising from the Study to the Company on adverse events, special situations including pregnancies and product quality complaints as defined within this exhibit. This safety information will be documented by the Investigator and reported as described in this exhibit from the time a subject has signed and dated an Informed Consent Form (ICF) until 30 days after the last dose of the Janssen Product(s) Under Study. All subsequent AEs and SAEs beyond 30 days after the last dose of the Janssen Product(s) under study shall be collected/reported if the investigator considers the AE/SAE to be causally related to the use of the Janssen Product(s) Under Study.

For the purposes of this Study, the Janssen Product(s) Under Study is (are):

DARZALEX FASPRO® (daratumumab hyaluronidase-fihj)

Maintenance of Safety Information: All safety data arising from the Study shall be maintained in a clinical database in a retrievable format. The Institution and Investigator shall provide a summary of all non-serious adverse events (NSAES) annually, and both serious and non-serious adverse events will be summarized in the final Study report (excluding those from subjects not exposed to a Janssen product). The summary shall include a listing of: Patient ID, adverse event term (uncoded), severity, relationship to Janssen Product(s) Under Study, and action taken with Janssen Product(s) Under Study. However, in certain circumstances more frequent provision of safety data may be

necessary, e.g. to fulfill a regulatory request, and as such the safety data shall be made available within a reasonable timeframe at the Company's request.

Follow-up: All (serious and non-serious) adverse events reported for a Janssen Product(s) Under Study shall be followed up in accordance with good clinical practice (GCP).

If batch/lot number is available, it must be reported. If batch/lot number is not available, it must be documented that it is not available. Without this documentation, Company is required to perform two follow-up attempts to obtain the batch/lot number.

#### **8.5.4.2 *Reporting of Safety data and Product Quality Complaints (PQCs) to Company***

All adverse events and special situations, whether serious or non-serious, related or not related, collected as per protocol design, following exposure to a Janssen Product(s) Under Study are to be documented by the investigator and recorded in the CRF and in the subject's source records. Investigators must record in the CRF their evaluation concerning the relationship of the adverse event to a Janssen Product(s) Under Study.

The Institution will submit (and procure that the Investigator submits), to the identified Company Representative in each Country/Territory the following safety information:

Type of report	Timelines	How to report
Serious Adverse Event,	Within 3 business days of becoming aware of the event(s)	By a secure means, as agreed by the Parties, on a Serious Adverse Event Form.
Adverse Events of Special Interest (AESI)	Within 3 business days of becoming aware of the event(s)	By a secure means, as agreed by the Parties, on a Serious Adverse Event Form.
Reports of drug exposure during pregnancy (maternal and paternal), with or without SAE.	Within 3 business days of becoming aware of the event(s)	By a secure means, as agreed by the Parties, on a Pregnancy Notification Form/Serious Adverse Event Form.
Reports of Suspected transmission of any infectious agent via administration of a Janssen Product, with or without an SAE	Within 3 business days of becoming aware of the event(s)	By a secure means, as agreed by the Parties, on a Serious Adverse Event Form.
Abnormal Pregnancy Outcomes (e.g. spontaneous abortion, fetal death, stillbirth, congenital anomaly, ectopic pregnancy)	Within 3 business days of becoming aware of the event(s)	By a secure means, as agreed by the Parties, on a Serious Adverse Event Form.
Special Situation (SS), if associated with an SAE	Within 3 business days of becoming aware of the event(s)	By a secure means, as agreed by the Parties, on a Serious Adverse Event Form.
Special Situation (not associated with an SAE)	Annually and in final study report.	Recorded in CRF and reported annually and in final study report.

Product Quality Complaints	Within 3 business days of becoming aware of the event(s)	By a secure means, as agreed by the Parties.
Non-Serious Adverse Event* (*Not meeting other listed 3 business day reporting criteria e.g. AESI or SS)	Annually and in final study report.	Recorded in CRF and reported annually and in final study report.
Follow-up information	Transmitted within the same timeframes as above i.e. if initial report was required to be submitted within 3 business days, follow-up information shall be submitted within the same timeframe.	Transmitted via same method as above i.e. if initial method of transmission was on an SAE form, follow-up information shall be transmitted in the same manner.

The Institution and/or Investigator is responsible for ensuring that these cases are complete and if not, are promptly followed-up. A safety report is not considered complete until all clinical details needed to interpret the case are received.

**Note:** In the event the Study is blinded, the Investigator will submit an unblinded SAE or pregnancy exposure report to Company.

If the Investigator/agent of the Investigator receives safety information and is aware it involves a non-study J&J product, it will be reported to Company, indicating it is an incidental spontaneous report discovered during the course of the study.

#### 8.5.4.3 ***Funder confirmation/review of SAEs***

Company Representative or designee will provide the Institution and Investigator with a list of the Study's SAEs (previously received by the Company from the Institution and the Investigator) on a semi-annual basis. Investigator will confirm to Company that all applicable SAEs related to Janssen Product(s) Under Study have been reported to Company. The principle investigator has the responsibility of reporting to the health authorities.

- **Funder Responsibilities**

Company Representative or designee will provide the Institution and Investigator with the following safety information:

- Refer to the Investigator's Brochure for the determination of expectedness.
  - <http://www.darzalex.com/shared/product/darzalex/darzalex-prescribing-information.pdf>
  - For DARZALEX® (daratumumab), the expectedness of an adverse event will be determined by whether or not it is listed in the Investigator's Brochure.

- any new information, which becomes available during the course of the Study, which may affect the overall safety profile of the Janssen Product(s) Under Study.
- ICF risk wording

#### 8.5.5 **Reporting of Pregnancy**

If a subject becomes pregnant during the study, in addition to reporting the pregnancy within 3 business days, a determination regarding Janssen Product(s) Under Study discontinuation and subject discontinuation must be made by the investigator in alignment with the protocol inclusion/exclusion criteria and in consultation with the reference safety information.

Because the effect of the Janssen Product(s) Under Study on sperm is unknown, pregnancies in partners of male subjects exposed to a Janssen Product(s) Under Study will be reported by the Investigator within 3 business days **of their knowledge of the event** using the Serious Adverse Event Form. Depending on local legislation this may require prior consent of the partner.

Follow-up information regarding the outcome of the pregnancy and any postnatal sequelae in the infant will be required.

### 8.6 **Halting Rules**

---

Temporary suspension of enrollment may occur for the following reasons:

- Significant delays in administration of daratumumab in the home due to logistical barriers.
- Infusion related reaction that occurs in the home that cannot be adequately managed.
- Recurrent lost medication.

## 9 Study Oversight

In addition to the PI's responsibility for oversight, study oversight will be under the direction of the SKCC's Data and Safety Monitoring Committee (DSMC). The SKCC DSMC operates in compliance with a Data and Safety Monitoring Plan (DSMP) that is approved by the NCI.

## 10 Clinical Site Monitoring and Auditing

Clinical site monitoring and auditing is conducted to ensure that the rights of human participants are protected, that the study is implemented in accordance with the protocol and/or other operating procedures, and that the quality and integrity of study data and data collection methods are maintained. Monitoring and auditing for this study will be performed in accordance with the SKCC's Data and Safety Monitoring Plan (DSMP) developed by the SKCC Data and Safety Monitoring Committee (DSMC). The DSMP specifies the frequency of monitoring, monitoring procedures, the level of clinical site monitoring activities (e.g., the percentage of participant data to be reviewed), and the distribution of monitoring reports. Some monitoring activities may be performed remotely, while others will take place at the study site(s). Appropriate staff will conduct monitoring activities and provide reports of the findings and associated action items in accordance with the details described in the SKCC DSMP.

## 11 Statistical Considerations

### 11.1 Study Hypotheses

The study hypothesis is that administration of daratumumab at home will improve patient satisfaction as compared administration of daratumumab in the infusion center.

### 11.2 Analysis Plans

For primary analysis, the SWT domain CTSQ scores after all cycles will be analyzed jointly in a linear mixed effects model with a random effect of patient and the fixed effect of the delivery mode (home vs. infusion center). Log or other transformation of CTSQ scores will be used, as appropriate, to satisfy the model assumptions. Possible time trends will be considered in the model and incorporated, if significant. The mean difference in CTSQ scores between home and infusion center will be computed with the corresponding 95% confidence interval and tested (null hypothesis of zero mean difference) using appropriate model-based contrast with alpha 0.05.

The same approach will be used for the secondary analysis of other CTSQ domains, EORTC QLQ-30, COST survey, and OOCAT survey scores.

The adherence at the home setting cycles will be analyzed in repeated measures logistic regression model with a random effect of patient and the fixed effect of the delivery mode (home vs. infusion center). The model will be used to compute the average rate of home setting adherence with the corresponding 95% confidence interval.

---

Secondary endpoints related to the barriers to home administration and exploratory endpoints related to the patient perceptions of home based anti-neoplastic therapy will be summarized using descriptive statistics.

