### **2.2.2 Secondary**

1. Adherence is defined as completing administration of medication in the home setting. Adherence will be measured for each dose given and failure would occur if the participant needs to go to the infusion center for administration for whatever reason. Based on previous studies of home based administration adherence rates over 75% would be needed to meet criteria for feasibility.
2. Measurement of quality of life will be measured using the EORTC QLQ-30.
3. Financial toxicity will be measured using the COST survey.
4. Safety will be evaluated through collection of adverse events, administration reactions related to Darzalex-Faspro.
5. Barriers to home administration will be measured through any delays in treatment related to delivery of medication, arrival time of the infusion nurse, issues related to storage of medication, issues related to administration of the medication.

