### **11.4 Sample Size Considerations**

The model-based contrast to be used for testing the primary null hypothesis is a generalization of the paired t-test to the case of more than one observation under each delivery mode (scores for 4 cycles at infusion center and 4 cycles at home). The proposed sample size of 20 patients provides 80% power to detect the minimally important difference of 5.9 points (Usmani et al, 2020) for CTSQ SWT domain score using the two-sided paired t-test with alpha 0.05 and assuming that the standard deviation of within patient differences is at most 8.92. Based on between-patient standard deviation of 13.76 for CTSQ SWT domain scores reported in Trask et al (2008), the standard deviation of within patient differences will be 8.92 or lower if the correlation between repeated score from the same patient is 0.79 or higher. The actual power will be higher since multiple observations per each delivery mode will be utilized in the linear mixed effects model.

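### Read plainly, the primary mixed model tests home against center on a pooled residual, not on patient-level error, so its 5% level rests on two assumptions the plan does not argue

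*Combined protocol and SAP*

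**What the plan says.** Section 11.2 puts the CTSQ SWT scores from all cycles into a "linear mixed effects model with a random effect of patient and the fixed effect of the delivery mode (home vs. infusion center". The difference between modes is "tested (null hypothesis of zero mean difference) using appropriate model-based contrast with alpha 0.05", with a 95% confidence interval. Time trends enter if significant. The section names no patient-by-mode random effect, residual covariance structure, robust standard error or degrees-of-freedom method.

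Section 11.4 says that this contrast "is a generalization of the paired t-test to the case of more than one observation under each delivery mode", with four cycles in each. It sizes the trial with a "two-sided paired t-test with alpha 0.05", "assuming that the standard deviation of within patient differences is at most 8.92", which it says holds "if the correlation between repeated score from the same patient is 0.79 or higher".

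For the other scores, 11.2 adds: "The same approach will be used for the secondary analysis of other CTSQ domains, EORTC QLQ-30, COST survey, and OOCAT survey scores".

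**The concern.** A paired t-test takes its error from how much the home-minus-center difference varies between patients. A random-intercept model with several scores per mode takes it from all variation left after removing each patient's mean and the common mode effect. The two agree in expectation only if patients do not differ in their response to home care and the cycle-to-cycle errors are independent. If either condition fails in the usual direction, the model's standard error is too small, the interval too narrow and the test too liberal. That would affect the primary conclusion and each secondary score handled the same way. Section 11.4 uses a single correlation and does not separate scores from the same site from scores across sites, so the plan neither supports the equal-effects condition nor shows its cost.

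**Working it through.** **Inputs.** From 11.4: n = 20, difference 5.9 points, SD of within-patient differences at most 8.92 (V = 8.92² = 79.57), between-patient SD 13.76, correlation 0.79, two-sided alpha 0.05, four scores per mode. From the Study Summary: order 2 center, 4 home, 2 center. Complete data are assumed throughout.

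**The plan's own figures.** 13.76 × √(2 × (1 − 0.79)) = 8.92. The exact noncentral-t power of the paired t-test is 80.1%, against the stated 80%. Both are reproduced.

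**One score per mode.** In a test dataset the random-intercept contrast and the paired t-test gave the same t (1.5928 in both), so the generalization wording is true in that case.

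**Four scores per mode.** Let τ² be the between-patient variance of the home effect and σ² the cycle residual variance, with τ² + 2σ² = V.

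- True variance of the mean contrast: (τ² + σ²/2)/20 = (σ² + 2τ²)/40. The paired test on patient means estimates this on 19 df.
- The random-intercept residual has 160 − 20 − 1 = 139 df. It pools the 19 df that carry σ² + 2τ² with 120 df that carry σ² alone: (19(σ² + 2τ²) + 120σ²)/139 = σ² + (38/139)τ². Its contrast variance averages (σ² + (38/139)τ²)/40.

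The two match only at τ² = 0.

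**Size under assumed shares p = τ²/V.** Type I error comes from 200,000 simulated trials per setting. Half-width is t × SE, with t = 1.977 (139 df) or 2.093 (19 df), at SD 8.92.

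| p | τ (points) | Random-intercept SE | True SE | Random-intercept type I | 95% half-width, model vs paired |
|---|---|---|---|---|---|
| 0% | 0 | 1.00 | 1.00 | 5.0% | 1.97 vs 2.09 |
| 5% | 2.0 | 0.99 | 1.07 | 7.1% | 1.95 vs 2.24 |
| 10% | 2.8 | 0.97 | 1.14 | 9.3% | 1.93 vs 2.38 |
| 25% | 4.5 | 0.94 | 1.32 | 16.2% | 1.86 vs 2.76 |

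Example at p = 10%: τ² = 7.96 and σ² = 35.80. The model SE is √((35.80 + 2.18)/40) = 0.97; the true SE is √((35.80 + 15.91)/40) = 1.14. The paired test on patient means stayed between 4.9 and 5.1% at every share. REML fits at p = 0 and 25% (400 trials each) gave 6.3 and 18.0%, in line with the table given their small number.

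With the cross-site correlation held at 0.79, the same-site correlation is 1 − σ²/13.76², which is 0.80, 0.81 and 0.84 at p = 5, 10 and 25%. The gap between the two correlations is small in each case.

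**Serial correlation alone.** With τ² = 0 and AR(1) residuals of 0.2, 0.4 and 0.6 in the 2-4-2 order, the random-intercept test rejects in 7.3, 9.2 and 9.8% of trials (a repeat run reached 10.0%). The paired test on patient means stays at 4.9 to 5.0%. Equal home effects are therefore necessary but not sufficient.

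**Power with patient-level error.** For 5.9 points at SD 8.92 and independent residuals, the paired test has power 99.8% (p = 10%), 98.9% (25%), 94.4% (50%) and 80.1% (100%).

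**The case against.** Four points deserve weight.

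- **Section 11.4 is not simply wrong.** A reader might infer that 11.2 and 11.4 contradict each other outright. They do not: the model does reduce to the paired t-test with one score per mode. What fails is narrower, namely that the patient-level error term is not kept with four.
- **The wording may allow more.** The appropriate model-based contrast of 11.2 could have been meant to include a random mode effect. It is certain only that no such term is named. A contrast is computed from the fitted model and adds no variance component, so the wording needs completing on either reading.
- **Heterogeneity is not shown.** Section 2.2.2 says: "Barriers to home administration will be measured through any delays in treatment related to delivery of medication, arrival time of the infusion nurse". A reader might infer that home effects therefore differ between patients. But these problems are recorded visit by visit. A late nurse at one cycle is residual noise, and becomes a patient-by-mode effect only if it recurs in the same patient. The documents do not say that it does.
- **The excess may be small.** If the shares refer to the variance of the four-cycle mean difference, 5 and 10% give only 5.5 and 6.0%. This is a 20-patient pilot, though one with a formal test at 0.05.

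All four limit the claim. None supplies the missing argument for equal effects and independent residuals.

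**Conclusion.** The point holds in limited form. As written, the primary interval and test are valid only under equal home effects and independent within-patient residuals, and the plan argues for neither. The algebra is firm. The size in this trial is unknown, because the documents do not split 8.92 into patient-by-mode variation and cycle noise and give no serial correlation. The range of 5.0% to about 16% for shares up to 25%, and about 7 to 10% under the AR(1) values tried, is illustrative and assumes complete data.

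A reader might go further and infer that the test is known to be invalid, or that the trial is underpowered. The first needs a variance that the documents do not give. The second is wrong: each patient's home-minus-center mean is an average of four single-score differences, so its SD cannot exceed 8.92 if each of them meets the plan's cap. N = 20 and the 80% statement stand.

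**What to change.** In 11.2, for the primary and secondary scores, base the home-versus-center contrast on patient-level error:

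1. With complete data, use a paired t-test on each patient's home mean minus center mean (19 df). A linear time trend cancels from this difference, because the average cycle number is 4.5 in both modes: (1 + 2 + 7 + 8)/4 and (3 + 4 + 5 + 6)/4.
2. When scores are missing, use a mixed model with a random patient intercept plus a random patient-by-delivery-mode effect, with Kenward-Roger or Satterthwaite degrees of freedom.
3. Fall back to the paired test if that model does not converge or the patient-by-mode variance is estimated at zero, since the model then collapses to the random intercept. In complete-data simulation with independent residuals, the estimate was zero in 53% of trials at a share of 0 and in 18% at a share of 10%.
4. The paired test needs at least one score in each mode, so report how many patients lack one.

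The change is wording only, with no added patients or data. The cost is a wider interval: a half-width of about 2.4 instead of 1.9 points at a 10% share and SD 8.92, and about 2.1 instead of 2.0 even if home effects are equal.

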**Description of Intervention:**

- 1) All participants included in the study will receive daratumumab subcutaneous injection therapy (fixed dose 1800mg). On study, participants will receive 2 cycles of daratumumab in the infusion center, followed by 4 cycles at home followed by 2 more cycles at the infusion center. At the beginning of each cycle, patient reported outcome surveys and quality of life surveys will be collected (EORTC-QLQ-30, CTSQ, COST, and OOCAT). During the infusion center phase, administration will be given by an infusion center nurse. During the home infusion phase of the study a home infusion nurse will administer darzalex-faspro. During home administration, specific details on barriers to maintaining adherence will be collected and described with descriptive analysis (i.e. issues with storage, delivery, disposal of medication).

**Study Duration:** 36 months

**Participant Participation Duration:** 10 months

**Estimated Time to Complete Enrollment:** 26 months

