## **3 Study Design**

### **3.1 Characteristics**

Open label, non-randomized trial in patients with multiple myeloma who are receiving DARZALEX FASPRO (daratumumab and hyaluronidase).

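### Section 11.2 adds time trends only if significant and does not give their form, although the fixed center-home-center order ties delivery mode to cycle number and strongly confounds it with a quadratic trend

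*Combined protocol and SAP*

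**What the plan says.** The Study Summary (Description of Intervention) gives one order for everyone: "receive 2 cycles of daratumumab in the infusion center, followed by 4 cycles at home followed by 2 more cycles at the infusion center". Section 3.1 calls the study an "Open label, non-randomized trial in patients with multiple myeloma", and section 3.5.1 marks randomization as not applicable, so no participant follows another sequence.

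Section 11.2 analyzes the CTSQ SWT scores from all cycles in a linear mixed model with a random patient effect and a fixed effect of delivery mode. The home-minus-center mean difference is tested "using appropriate model-based contrast with alpha 0.05". The only provision for time is this sentence: "Possible time trends will be considered in the model and incorporated, if significant". The form of trend, the significance level and the order of testing are not stated. The same approach carries over to the other CTSQ domains and to the EORTC, COST and OOCAT scores.

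Section 11.4 makes no allowance for a trend term. It states: "The proposed sample size of 20 patients provides 80% power to detect the minimally important difference of 5.9 points".

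**The concern.** With a single sequence, mode is a function of cycle number, so the form of trend decides how much information about home remains. A home block in the middle of the study looks like a hump over time. A real home effect can therefore pass for curvature, and chance curvature that passes a significance test pulls the mode estimate with it.

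The plan leaves both the form and the inclusion of the trend to be settled on the same data as the primary test. Two analysts following section 11.2 faithfully could reach different standard errors and different p-values, and one of the permitted routes does not hold the 0.05 level.

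**Working it through.** **Inputs.** From section 11.4: 20 patients, 4 center and 4 home scores each, difference 5.9, SD of within-patient differences 8.92, between-patient SD 13.76, correlation 0.79, two-sided alpha 0.05. From the Study Summary: the order of modes. Assumed, because the documents do not say: a 0.05 level for the trend test, and the size of any real curved trend.

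**The plan's own figure.** SD of differences = 13.76 × √(2 × (1 − 0.79)) = 8.92. Paired t-test: noncentrality = (5.9 / 8.92) × √20 = 2.96 on 19 df, giving power 80.1%. Both figures reproduce.

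**Residual SD per score.** 13.76 × √(1 − 0.79) = 6.31.

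**Overlap of mode with time.** Let t be centered cycle (−3.5 to 3.5) and mode = 0,0,1,1,1,1,0,0.

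- Linear: mean cycle is 4.5 in both modes, so the correlation is 0 and variance inflation is 1.
- Quadratic: t² averages 1.25 in home cycles and 9.25 in center cycles. The cross-product with mode is −16, and the sums of squares are 2 (mode) and 168 (t²). Correlation = −16 / √(2 × 168) = −0.87. Variance inflation = 1 / (1 − 256/336) = 4.2.
- Cycle as a factor plus mode: 9 columns with rank 8, so the separate mode coefficient is aliased. The contrast mean(C3–C6) minus mean(C1, C2, C7, C8) can still be computed, with SE = 6.31 × √((1/4 + 1/4) / 20) = 1.00.

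**Standard error and power at 5.9 points.** With mode alone or mode plus linear: SE = 6.31 / √(20 × 2) = 1.00, power above 99.9%. With linear and quadratic always included: SE = 1.00 × √4.2 = 2.04, power about 82%.

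**Effect of the significance rule.** Simulation of 20,000 trials per scenario, complete data, Monte Carlo error about 0.2 points near 5%.

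- No home effect, no trend, linear kept if significant: type I error 5.0%.
- Same, quadratic kept if significant with mode in the model: 7.4% (7.6% in a separate run of 6,000 trials).
- Same, quadratic tested with mode left out: 2.5%.
- True 5.9-point home effect, no trend, quadratic tested with mode in the model: power 97.8%.
- Same, quadratic tested with mode left out: it enters in 99.9% of trials and power falls to about 82%. A cycle factor tests significant in 99.6%.

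**A real curved trend with no home effect.** A quadratic hump of 3 points, peak to trough over the eight cycles, biases an estimate without a quadratic term by 3 × (9.25 − 1.25) / (12.25 − 0.25) = 2.0 points. Percentage of trials calling home significant, over an assumed range of humps:

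| Hump (points) | Linear always, no quadratic | Quadratic if significant, mode in model | Quadratic always |
|---|---|---|---|
| 0 | 5.0 | 7.4 | 4.9 |
| 1 | 10.1 | 12.1 | 4.8 |
| 2 | 26.1 | 25.7 | 4.8 |
| 3 | 50.9 | 43.4 | 5.1 |
| 4 | 74.8 | 54.2 | 5.0 |
| 6 | 97.7 | 40.7 | 5.0 |

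**Incomplete data.** The linear balance is lost for a patient who stops early: the correlation of mode with cycle is 0.29 after C7 and 0.83 after C6. In runs with 4 to 8 of 20 patients stopping after C6, type I error under the linear reading stayed at about 5 to 6%, so the point does not rest on dropout.

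**The case against.** The other side has a good deal in its favor.

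- The simplest meaning of a time trend is a straight line. The 2-4-2 order balances that exactly, and the rule then holds 5.0%. A reader might infer that the rule breaks alpha whatever trend is considered; the documents do not support that.
- Section 11.2 defines the model with mode in it and then considers trends within that model. Testing the trend without mode is possible under the text but fits it less well, so the fall to 82% power is the less likely route.
- A reader might infer that the home effect becomes inestimable. That is too strong. A quadratic leaves about 24% of the variance of mode free, and 82% power still meets the planned 80%. Section 11.4 treats 0.79 as the lowest correlation; at 0.85 and 0.90, power with the quadratic always included is about 92% and 99%. In a by-cycle model only the separate mode coefficient is lost, and the mean difference that section 11.2 names can still be computed.
- A reader might infer that the rule creates the confounding with a real curved trend. The single sequence does that. With a 3-point hump, a linear-only model gives more false positives (51%) than the current rule (43%), so banning a quadratic outright would leave that bias unseen.
- This is a 20-patient, single-site pilot.

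All of this stands as a limit on the size of the point. It does not answer the point itself: the plan does not say linear only, and it lets the data choose among forms with very different consequences for the primary contrast.

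**Conclusion.** The point holds in a limited form. The trend rule for the primary model is not prespecified, in a design where the choice of trend matters. Under the linear reading there is no harm with complete data. Under the quadratic reading with mode in the model, type I error is about 7.4 to 7.6% in place of 5%. If the trend were tested without mode, the test would be conservative (2.5%) and a true 5.9-point effect would be tested with about twice the standard error (2.04 against 1.00) and about 82% power in place of nearly 100%.

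These figures rest on the SD and correlation in section 11.4, complete data, a constant home effect and an assumed 0.05 level for the trend test. Bias from a real curved trend is a separate limitation of the single sequence, and no choice of model fully removes it.

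**What to change.** Replace the time-trend sentence in section 11.2 with: *A linear effect of cycle number (1-8) will be included in the primary model regardless of significance; no other time term will be selected on the data.* Apply the same rule to the secondary scores analyzed in the same way.

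Add three things:

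- a prespecified sensitivity analysis with linear and quadratic cycle terms always included, noting its wider interval;
- a table or plot of mean SWT by cycle;
- a statement that a curved time effect cannot be cleanly separated from the home effect in this single-sequence design.

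With complete data, the primary model then has type I error 5.0%, SE about 1.00 and power above 99.9% at 5.9 points. When patients stop early, the linear term also adjusts for the lost balance. The cost is one degree of freedom and a few lines of text, with no change to visits, sample size or data collection. The downside is that the linear primary model stays exposed to bias from a real curved trend; the sensitivity analysis is there to show it.
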